### 6.2. Calculations Using Dates

Age will be calculated as:

$$\text{Age} = \text{Integer}((\text{Date of enrollment} - \text{Date of Birth})/365.25)$$

Study Day will be calculated as

$$\text{Study Day} = \text{Integer}(\text{Date of Event} - \text{Day 1 of Treatment}) + 1$$

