3. INVESTIGATIONAL PLAN

3.1. Overall Study Design

This is a Phase 3, double-blind, placebo-controlled, randomized, multicenter study to evaluate the efficacy, safety, and tolerability of Cannabidiol Oral Solution (CBD) as adjunctive therapy with vigabatrin as initial therapy, compared to vigabatrin alone in the treatment of infants newly diagnosed with Infantile Spasms (IS). Randomization will occur during Visit 2 and then allocated to one of two treatment groups:

- Treatment with vigabatrin plus
- CBD 40 mg/kg/day, or
- Matching CBD 40 mg/kg/day placebo

Approximately, 190 patients in total will be enrolled into one of the two treatment arms; 130 patients in the investigational product arm with 60 patients in the placebo arm. Patients will be dosed approximately every 12 hours with meals to help ensure consistent plasma levels are achieved and to reduce variability.

Doses of CBD exceeding 40 mg/kg/day will not be examined in this study. In addition to the safety assessments required by the study protocol, the investigator will monitor patients throughout the study as recommended in the approved product label for vigabatrin. Study participants will be newly diagnosed pediatric patients age 1 to 24 months (inclusive) experiencing infantile spasms who satisfy all inclusion/exclusion criteria. This study will be comprised of five periods: Screening, Initial Treatment, Extended Treatment, Taper, and Follow-up Periods, with a maximum duration of approximately 140 days.

The study design and patient progression through the study is outlined in [Figure 1](#). All screening, efficacy, and safety evaluations will be performed according to the schedule of assessments summarized in [Table 1](#).

Each newly diagnosed patient with Infantile Spasms will complete a Screening Period and will have up to 14 days to enroll in the study.

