3.2.1. Inclusion Criteria

All patients must satisfy the following criteria to be considered for study participation:

1. Parent(s)/caregiver(s) fully comprehend and sign the informed consent form, understand all study procedures, and can communicate satisfactorily with the investigator and study coordinator, in accordance with applicable laws, regulations, and local requirements.
2. Male or female between 1 months to 24 months of age (inclusive) at time of consent.
3. Clinical diagnosis of infantile spasms, confirmed by video-EEG analysis (including at least one cluster of electroclinical spasms [≥ 3 in any 10-minute epoch]) and hypsarrhythmia) obtained during the Screening Period and read by a central reader.
4. General good health (defined as the absence of any clinically relevant abnormalities as determined by the investigator) based on physical and neurological examinations, medical history and clinical laboratory values completed during the Screening Visit (Visit 1).
5. In the opinion of the investigator, the parent(s)/caregiver(s) is (are) willing and able to comply with the study procedures and visit schedules.

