## 3.2. Selection of Study Population

### 3.2.1. Inclusion Criteria

#### Diagnosis and main criteria for inclusion:

Patients will be male and female patients between 3 and 12 months of age (inclusive), with a new clinical diagnosis of Infantile Spasms, confirmed by video-EEG analysis during the Screening Period, have adequate renal and hepatic function and who meet all the inclusion and none of the exclusion criteria. Parent(s)/caregiver(s) must be able to understand and provide written consent.

All patients must satisfy the following criteria to be considered for study participation:

1. Parent(s)/caregiver(s) fully comprehend and sign the informed consent form, understand all study procedures, and can communicate satisfactorily with the investigator and study coordinator, in accordance with applicable laws, regulations, and local requirements.
2. Male or female between 3 months to 12 months of age (inclusive) at time of consent.
3. Clinical diagnosis of infantile spasms, confirmed by video-EEG analysis (including at least one cluster of electroclinical spasms [ $\geq 3$  in any 10-minute epoch]), hypsarrythmia or a pattern of epileptic encephalopathy) obtained during the Screening Period and read by the Investigator.
4. General good health (defined as the absence of any clinically relevant abnormalities as determined by the investigator) based on physical and neurological examinations, medical history and clinical laboratory values completed during the Screening Visit (Visit 1).
5. In the opinion of the investigator, the parent(s)/caregiver(s) is (are) willing and able to comply with the study procedures and visit schedules.

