## **9. BASELINE SUBJECT DATA**

### **9.1. Baseline Demographic and Physical Characteristics**

Demographic and baseline characteristics (including age in months, gender, race, ethnicity, length, weight, BMI, head circumference, video-EEG results) will be summarized for both the Safety and ITT Populations. All demographic and baseline characteristics along with body mass index (BMI) will be listed for the Safety Population.

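### The SAP derives age in completed years, but its baseline tables call for age in months in a population of infants

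*SAP*

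**What the plan says.** SAP 6.2 (Calculations Using Dates) introduces the rule with "Age will be calculated as" and sets age equal to Integer((enrollment date − birth date)/365.25). The first date in the formula is the "Date of enrollment". No unit is named.

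SAP 9.1 (Baseline Demographic and Physical Characteristics) says the characteristics to be summarised for both the Safety and ITT Populations are those "including age in months, gender, race, ethnicity, length, weight, BMI, head circumference, video-EEG results".

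On who is eligible, protocol 3.2.1 has "Male or female between 1 months to 24 months of age (inclusive) at time of consent". SAP 3.2.1 still has "Male or female between 3 months to 12 months of age (inclusive) at time of consent"; the SAP Introduction states that it is based on protocol version 2.0 of 30 October 2017. Protocol 3.1 adds that each patient "will have up to 14 days to enroll in the study".

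SAP 10.2 plans a comparison of baseline values between treatment groups. Potentially important imbalances may be carried into the efficacy analysis as covariates, with supportive subgroup analyses where appropriate.

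**The concern.** Dividing days by 365.25 gives years, and taking the integer part discards the fraction. In a trial of adults that is the usual age variable. Here all or nearly all patients are under two years old, so the fraction is where the information lies. Section 6.2 therefore cannot produce the variable that section 9.1 asks for, and a programmer has to depart from one or the other.

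If section 6.2 is followed, age in the demographic table becomes a near-binary variable, or close to a constant if most patients are under one year. The comparability check in SAP 10.2 could then not see a difference between, say, an arm of mostly 4-month-olds and an arm of mostly 10-month-olds. Any adjustment for age prompted by that check would be equally blind to it.

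**Working it through.** **Inputs.** Formula: SAP 6.2. Unit required: months, SAP 9.1. Age range: 1 to 24 months (protocol 3.2.1) or 3 to 12 months (SAP 3.2.1). Time to enrollment: up to 14 days (protocol 3.1); the SAP design summary allows 14 (± 5) days of screening, so up to 19. The plan gives no figure of its own to reproduce.

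**Single ages.** Integer(days/365.25), with one month taken as 365.25/12 = 30.4375 days for the rows given in whole months:

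| Age | Days | Days/365.25 | Recorded age |
|---|---|---|---|
| 4 months | 121.75 | 0.33 | 0 |
| 10 months | 304.4 | 0.83 | 0 |
| First birthday, 365 days | 365 | 0.9993 | 0 |
| First birthday, 366 days | 366 | 1.002 | 1 |
| 13 months | 395.7 | 1.08 | 1 |
| 23 months | 700.1 | 1.92 | 1 |
| Second birthday, 730 days | 730 | 1.9986 | 1 |
| Second birthday, 731 days | 731 | 2.0014 | 2 |

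**All birth dates.** The formula was applied to each of the 1,461 birth dates in a four-year calendar cycle:

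- 1 to 11 completed months, on the monthly birthday: 0 for every birth date.
- Exactly 12 months: 0 for 1,096 birth dates, 1 for 365.
- 13 to 23 months: 1 for every birth date.
- Exactly 24 months: 1 for 731 birth dates, 2 for 730.

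**Shares over a range, if ages were spread evenly.** As a rough check on 1 to 24 months, (12 − 1)/23 = 48% are coded 0 and (24 − 12)/23 = 52% are coded 1. Counting every day of age for every birth date:

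| Range | Coded 0 | Coded 1 | Coded 2 |
|---|---|---|---|
| Protocol, 1–24 months | 47.9% | 52.1% | 0.07% |
| Protocol, upper limit + 14 days to enrollment | 46.9% | 51.0% | 2.0% |
| SAP, 3–12 months | 99.9% | 0.1% | none |
| SAP, upper limit + 14 days | 95.1% | 4.9% | none |
| SAP, upper limit + 19 days | 93.5% | 6.5% | none |

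**Candidate replacement.** Integer(days/30.4375) can read one month low on a monthly birthday: 365/30.4375 = 11.99, so an exact first birthday truncates to 11 for 1,096 of 1,461 birth dates. Rounding to one decimal gives 12.0 there. Short calendar months still show: 28/30.4375 = 0.92, displayed as 0.9 for a child of exactly one calendar month. Completed calendar months avoid both problems.

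**The case against.** The best reply is that this is a conflict of units with a natural resolution. The section governing the baseline table specifies months, date of birth is collected (protocol 6.2.1, SAP 5.1), and a competent programmer would query the formula or follow the table. On that view nothing is lost for good. This stands as far as it goes: age in months can be rebuilt at any time. It does not remove the fault, because the only derivation written down gives the wrong variable.

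A reader might also infer more than the documents support:

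- *That age eligibility could not be verified.* Eligibility is judged at consent, date of birth is recorded, and SAP section 8 lists eligibility criteria separately. Nothing says the derived age is used for that purpose.
- *That a planned efficacy analysis is damaged.* The primary comparison is unadjusted: chi-square in protocol 8.4.3.1, Fisher's exact test in SAP 10.6.1. The named ANCOVA covariates are baseline CGI-S and baseline spasm-free days, and SAP 10.4 plans no subgroup analysis. Age enters only through the conditional check in SAP 10.2.
- *That 48% and 52% describe the expected sample.* They rest on an even spread over the protocol's range. Protocol 1.4 says the disease typically strikes in the first year of life, so the share coded 0 could well be higher.
- *That using the enrollment date is an error because eligibility refers to consent.* Age at enrollment is a legitimate descriptive variable, and no section requires the summary to use consent. The choice only needs to be stated.

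**Conclusion.** The inconsistency is real and lies within the SAP: section 6.2 yields completed years and section 9.1 requires months. That every infant under 12 months is recorded as 0 follows from the formula alone and needs no assumption about the age distribution. The percentages do assume evenly spread ages and are illustrations, not forecasts. They also depend on which age range applies. The SAP's narrower range makes the loss greater, since age becomes almost a constant.

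The reach is limited to the baseline age summary and the conditional comparability and adjustment step in SAP 10.2. The primary result, sample size, power and alpha do not depend on it, and no data are lost. This is a minor point, worth correcting because the written rule gives a wrong result and the correction is free.

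**What to change.** In SAP 6.2, replace the formula with age in completed calendar months from date of birth to a named reference date, and state the unit and that completed months are counted. If a decimal age is preferred, use (reference date − date of birth)/30.4375, explicitly rounded rather than truncated to one decimal, and accept that a child on an exact monthly birthday may show slightly under the whole month. Either enrollment or consent can be the reference date, provided it is named.

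When the SAP is next revised, its 3 to 12 month age range should also be reconciled with the current protocol's 1 to 24 months.

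The cost is one line of text and a trivial programming change before database lock. No new data, visits or protocol amendment are needed.

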### 6.3. Baseline

The Baseline value for any measurement will be the most recent valid value prior to the first dose of study medication.

#### 6.3.1. Visit Windows Relative to the First Dose of Study Medication

**Table 2: Visit windows and target days**

Visit	Relative Target Day	Visit Window
Visit 1 (Screening)	-14	-14 – -1
Visit 2	Day 1	1
Visit 3	4	4
Visit 4	13	13
Visit 5 (End of Study)	14	14
Visit 6	Week 6	
Visit 7	Week 10	
Visit 8 (End of Study)	Week 13	
Early Withdrawal		
Taper Period		3 days
Followup Period		30 days

## 6.4. Analysis Populations

### 6.4.1. Safety Population

The Safety Analysis Population will include all subjects who were treated with at least one dose of the study drug. The Safety Analysis Population will be used for all safety assessments.

### 6.4.2. Intent to Treat Population

The Intent to Treat (ITT) Population will include all subjects who randomized. The ITT will be used for all efficacy assessments.

### 6.4.3. PK Analysis Population

The PK Analysis Population will include all subjects who were treated with at least one dose of the study drug and have at least one usable plasma concentration measurement.

### 6.4.4. Handling of Missing Values

There will be no imputation of the missing values. All assessments will be conducted based on all observed data. A sensitivity analysis will be conducted to assess the impact of the missing values on the final analysis.

Partial missing dates will be imputed as described in Table 3. After following these imputation rules, if the start date is imputed as a date after the end date, the start date will be set to the end date to provide a positive duration for the event incidence.

**Table 3: Calculation of missing or partially missing dates**

Missing Start Date Portion	Prior to Treatment	Same as Treatment Start Date	After Treatment Start Date
Day	Month and Year < Month and Year of first treatment:	Month and Year = Month and Year of first treatment:	Month and Year > Month and Year of First Treatment:
Day and Month	Day = 1 Year < Year of first treatment:	Day = Day of first treatment Year = Year of first treatment:	Day = 1 Year > Year of first treatment:
Day, Month, and Year	Day = 1, Month = July	Day = Day of first treatment, Month = Month of first treatment	Day = 1, Month = January
	To be conservative, completely missing start dates will be set to the date of first treatment		

## **7. DATA PRESENTATIONS AND DATA MANAGEMENT**

### **7.1. Data Presentations**

The templates provided with this SAP describe the presentations for this study and therefore the format and content of the summary tables, figures and listings to be provided.

### **7.2. Data Management**

Data management for this study will be the responsibility of the CRO as described in the Data Management Plan.

### **7.3. General Post Text Summary Table and Individual Subject Data Listing Format Considerations**

## **8. PATIENT DISPOSITION AND PROFILE OF SCREEN FAILURES**

The number of patients in the ITT and Safety Analysis Population will be summarized along with reasons for early discontinuation from the study. A summary table of protocol deviations will also be presented. All protocol deviations along with patient's eligibility criteria will be listed for the Safety Analysis Population.

Discontinuation reasons are as follows:

- Inadvertently enrolled (enrollment criteria not met)
- Investigator decision
- Adverse Event
- Subject withdrew consent
- Lack of protocol compliance
- Subject attempted suicide or is at risk of suicide
- Sponsor decision
- Subject becomes pregnant
- Abnormal laboratory values
- Lost to follow-up
- Death
- Other

The following important (clinically) protocol deviations, as identified in the clinical trial management system (CTMS), will be summarized:

- Administrative Criteria
- Eligibility and Entry Criteria
- IP Compliance
- Informed Consent
- Laboratory Assessment Criteria
- Serious AE Criteria
- Study Procedures Criteria
- Regulatory or Ethics Approvals Criteria
- Visit Scheduled Criteria
- Other Criteria

Supportive listings will also be provided:

- Allocation to treatment
- Protocol deviations
- Subjects eligibility criteria

### **8.1. Patient Accounting**

Patients who are randomized will be listed and summarized including number of patients randomized (ITT), treated (Safety Population), in PK Population, and number and reason for discontinuation.

**8.1.1. Patient Accounting by Treatment Group**

Patients who are randomized will be listed and summarized by treatment group including number of patients randomized (ITT Population), treated (Safety Population), in PK Population, and number and reason for discontinuation.

**8.1.2. Patient Distribution by Investigator**

Patients who are randomized will be listed and summarized by investigator, including number of patients randomized (ITT Population), treated (Safety Population), in PK Population, and number and reason for discontinuation.

**8.2. Screen Failure**

Patients who fail screening and are not eligible for the study will not be entered into the database.

## **9. BASELINE SUBJECT DATA**

### **9.1. Baseline Demographic and Physical Characteristics**

Demographic and baseline characteristics (including age in months, gender, race, ethnicity, length, weight, BMI, head circumference, video-EEG results) will be summarized for both the Safety and ITT Populations. All demographic and baseline characteristics along with body mass index (BMI) will be listed for the Safety Population.

### **9.2. Medical History and Medical Conditions Present at Entry**

Medical and surgical history will be coded using the MedDRA, version 20.0 or above, and will be summarized by system organ class and preferred term for the Safety Population.

Development will be summarized as ‘high’ or ‘low’ risk of developmental impairment as defined by the International Collaborative Infantile Spasms Study (ICISS) for the Safety Population. ICISS criteria include the presence or absence of the following factors that increase the risk of developmental impairment: chromosomal abnormality or clinical syndrome, neonatal encephalopathy with seizures, and cerebral palsy or developmental impairment diagnosed before onset of spasms.

### **9.3. Prior Medication History and Medications Present at Entry**

Prior and concomitant medications will be coded using World Health Organization Drug Dictionary (WHO-DD), version March 2017 and will be summarized separately by preferred term for the Safety Population. The details of medication and foods excluded from the study are presented in the protocol. At each level of summarization, subjects reporting more than one medication will be counted only once.

Summary tables and listings will include Baseline assessment data.

#### **9.3.1. Non-Diagnosis Related Prior Medication History**

Prior non-diagnosis related medications are classified as medications which stopped before the date of first dose of study medication while concomitant medications are medications started prior to, on or after the first dose of study medication, and ended on or after the date of first dose of study medication or were ongoing at the end of the study. At each level of summarization, subjects reporting more than one medication will be counted only once. Summary tables and listings will include Baseline assessment data.

#### **9.3.2. Prior Diagnosis Related Medication History**

Patients with prior anti-epileptic drug administration will be excluded from this study.

#### **9.3.3. Missing and Partially Missing Start and Stop Dates**

Imputation of missing dates is described in [Section 6.4.4](#).

#### **9.4. Baseline Physical Examination**

Results of the Screening Visit complete physical examination will be listed and summarized by treatment group for both the Safety and Efficacy Population. General appearance, ears, eyes, nose, and throat (EENT), heart, peripheral vasculature, lungs, musculoskeletal system, abdomen, neurologic function, endocrine system, and skin will be assessed and summarized as 'normal' or 'abnormal'. Height/length and weight will be summarized and BMI calculated.

#### **9.5. Baseline Vital Signs**

Baseline Vital Signs will be defined as the most recent valid measurement taken before receiving the first dose of medication during Visit 3 (Treatment Period Day 1). Vital signs will be summarized for both the Safety and ITT Population. Vital signs will consist of blood pressure, pulse rate, temperature, and respiration rate measurements.

#### **9.6. Baseline Laboratory Data**

Results of the Screening Visit laboratory values will be summarized for both the Safety and ITT Population. Hematology assessments include: hemoglobin, hematocrit, total and differential leukocyte count, red blood cell (RBC), and platelet count. Serum chemistry assessments include: albumin, blood urea nitrogen (BUN), creatinine, total bilirubin, alkaline phosphatase (ALP), aspartate transaminase (AST), alanine transaminase (ALT), sodium (Na+), potassium (K+), chloride (Cl), lactate dehydrogenase (LDH), uric acid, glucose, and calcium.

The results of the Screening Visit drug screen will be listed for the Safety Population, to include amphetamines, barbiturates, tricyclic antidepressants, cocaine, methadone, morphine, 3,4-methylenedioxymethamphetamine (ecstasy), THC, phencyclidine, cotinine, alcohol, and opiates. Presence of any drugs will be considered a screen failure.

Urinalysis will only be assessed during the Screening Visit and will be summarized for both the Safety and ITT Population. Urine assessments include: pH, specific gravity, protein, glucose, ketones, bilirubin, blood, nitrite, leukocyte esterase, and urobilinogen. If protein, occult blood, nitrite, or leukocyte esterase values are out of range a microscopic examination will be performed and results provided as a listing.

#### **9.7. Baseline Primary and Secondary Efficacy Evaluations**

The primary objective of this study is to evaluate the efficacy of Cannabidiol Oral Solution as adjunct therapy to vigabatrin in treating infantile spasms. Efficacy will be evaluated using the following primary and secondary endpoints.

##### Primary Efficacy Analysis

- Percent of patients with resolution of both infantile spasms and hypersarrhythmia or a pattern of epileptic encephalopathy at Day 14 (complete response) will be compared between Vigabatrin plus Placebo and Vigabatrin plus CBD 40 mg/kg/day groups.

### Secondary Efficacy Analyses

- Percent of patients with resolution of infantile spasms at Day 14 will be compared between treatment groups.
- Percent of patients with resolution of hypsarrhythmia or a pattern of epileptic encephalopathy at Day 14 will be compared between treatment groups.
- Investigator impression of efficacy and tolerability of study drug (Clinical Global Impression – Global Improvement (CGI-I)) will be compared between treatment groups.
- Percent reduction in spasm-free days between the Initial Treatment Period (Days 1 to 14) and Screening Period (Days -14 to -1) will be compared between treatment groups.
- Percent of patients who relapse during the Extended Treatment Period will be compared between 14-day Vigabatrin + CBD responders and 14-day Vigabatrin + placebo responders. Time to relapse will be calculated and compared.
- Percent of patients with partial response at Day 14 who achieve complete response during the Extended Treatment Period will be compared. Time to complete response will be calculated and compared.

Baseline Video-EEG results (Presence of spasms, number of spasms, and presence of hypsarrhythmia, presence of epileptic encephalopathy) will be summarized by treatment group for both Awake and Sleep periods.

Historical seizure history will be recorded during the Screening Visit based on parent/caregiver recollection. Baseline percent of spasm-free days will be calculated using the seizure diary collected during the Screening Period and summarized by treatment arm.

